## **Study Design and Methods**

**Methods:** *Describe, in detail, the research activities that will be conducted under this protocol:*

### **Informed Consent Process**

Screening eligibility and study enrollment for all phases of the research will occur either online via the study's webpage, in person, or by phone or mail. All advertisements will contain the study: toll-free phone number, email address, and Qualtrics' website link. Individuals will be provided a brief description of the study, and then screened in person or by phone. For further information, they can be sent a link to the study website. The website will contain a short description of the study as well as eligibility questions. Qualtrics (<https://www.qualtrics.com>) is a secure, online, HIPAA-compliant survey software that transmits data to and from secure firewalled data centers using Transport Layer Security encryption. We successfully used this software to obtain informed consent and to administer a tobacco use and health behavior survey study in a rural AK region with over 400 adult participants (57% AN persons). The potential research participant will be informed of the details of the study and the fact that participation is entirely voluntary and will not affect their current or future medical care at the Alaska Native Tribal Health Consortium (ANTHC) or Mayo Clinic medical facilities. The potential research participants will be given the opportunity to have any questions about the study answered and will have as much time as they need for the consent process. If anyone is

uncomfortable completing their survey via Qualtrics, they will be given the option to complete their surveys by email, phone, or in person with assistance from a study team member.

Verbal Consent: For phases 1, 2 and the supplemental aim, the research presents no more than minimal risk to subjects and involves no procedures for which written consent is normally required outside of the research context. If the potential participant is eligible and verbally consents to participate they are enrolled.

[figure not shown]
Written Consent: For phases 3 and 4, if the potential participant is eligible to participate, they will complete the informed consent in person, by mail or email, or on-line. If consent is completed on-line, to ensure they review the document, their understanding of the consent form will be assessed online through multiple choice questions with required answers before being able to proceed with the study. Questions are based on those used in studies with potentially vulnerable participants. Any wrong answers during the consent will be sent to study staff who will contact the potential participant via email or phone for clarification. For those who complete their consent by mail, A study team member will mail the consent form to the participant to review, sign, and mail back in the enclosed postage-paid return envelope. Those who wish to complete consent by DocuSign, but experience difficulty, will be provided support by a study team member to complete the DocuSign process. Eligible individuals completing the informed consent process will be enrolled.

The potential research participant will be informed of the details of the study and the fact that participation is entirely voluntary and will not affect their current or future medical care at the Alaska Native Tribal Health Consortium (ANTHC) or any tribal or Mayo Clinic medical facilities. All screening and consent forms/processes are approved by the Alaska Area IRB and are at the eighth grade reading level. Computer software programs are used to test the reading level of each document. Individuals will be given an opportunity to ask questions and decide whether or not s/he wishes to participate. The consenting software is designed to ensure that all participants meet the inclusion/exclusion criteria as stated in the study protocol and that the potential participant clearly understands the study procedures and agrees to follow them. Prior to survey administration, potential participants will be able to receive a copy of the consent information for their records. If they agree to participate they will select to proceed to the web survey, or exit if they choose to decline. The consent form will include information on the nature of the study and alternatives to taking part, and contact information (toll-free number) for the PIs of the study. Participants will be encouraged to phone with concerns or problems that might occur during the study.

Standard language in our consent procedure assures the study participants of the confidential nature of the study. Those who participate will be clearly told that they may withdraw from the study at any time without adversely affecting their current or future medical care at the Alaska Native Tribal Health Consortium (ANTHC) or any tribal or Mayo Clinic medical facilities. These standards are strictly adhered to and monitored by the Alaska Area IRB and the Mayo IRB

# Figure 1: CAN Quit Study Flowchart

Connecting Alaska Native Smokers to Quit

## Formative Work to Develop the Intervention: Aim 1 (Phases 1-3)

### Projected Content and Structure for the Facebook Intervention

Structure and duration. The intervention will consist of a Facebook group moderated by an AN facilitator. To address potential concerns about Facebook privacy, we will utilize a closed and secret Facebook group and a group policy/guideline that emphasizes confidentiality of all content. A secret group is defined as invitation only, with the group and content not visible to anyone on Facebook except participants. Thus, anyone searching on Facebook would not find the group nor be able to request to join. Also, group membership or postings through newsfeeds will not be visible on the participants' personal Facebook page.

We chose to use a moderated group based on research indicating that moderators play a critical role in directing and tailoring content to the group and enhancing overall social media engagement. Also, the frequency of moderator Facebook postings is associated with increased participant engagement.

The Facebook group will be active for 3 months. A content library of moderator postings will be developed for posting within the Facebook group for the 3 months that the group is active. The moderator will check-in with the group about 3-4 times daily to respond to comments and other user-generated content, and to prompt and direct discussions by encouraging participants to share stories about their tobacco use journey. Participants will be notified through news feeds when there is new Facebook content posted.

Content for moderator postings. Moderator postings will be developed from two existing sources.

First are the CDC Tips™ campaign digital story videos. The 31 stories are based on factual appeals to quit smoking and each is about 2.5 minutes long. The stories address different phases of the quitting process, specifically: motivation (why to quit), engaging in treatment (how to quit), and relapse prevention. We anticipate creating about 8-10 new digital stories featuring AN persons. However, based on formative work, we recognize that existing Tips™ stories such as Michael's story (AN former smoker) may be acceptable, and will be included. The digital stories will be embedded in moderator postings as YouTube links.

Second, for additional content for moderator postings, we will tailor existing postings from a recently held CDC Facebook event "30 Smoke-free Days" that invited people nationwide to set a quit date and targeted adults ages 18-54 years. A moderator posted once daily for 30 days. These general audience moderator postings included images combined with text that were inspirational, celebrated quitting milestones, and included embedded YouTube links to specific Tips™ videos. The content is consistent with clinical practice guidelines for behavioral strategies to motivate, prepare and assist individuals to quit smoking, and stay tobacco free. In an uncontrolled evaluation, over a 1-month period, 3,221 people nationwide received updates and posts from the Facebook page, and of these, 641 (20%) actively participated by making a quit attempt or supporting others to quit. The mean total engagement (likes, shares, replies, comments) on event content was high (36%) compared to the average monthly engagement rate of 4-6% on the CDC main Facebook wall. Moderator postings with the highest level of engagement, defined as discussion and participant sharing, were themes related to lack of family support, weight gain, and cravings.

For cultural tailoring, messaging will center on abstinence from all tobacco and nicotine products, including *ST/iqmik* and e-cigarettes. Differentiating ceremonial/traditional tobacco use from commercial use is not an issue as prior work documents that AN people do not use tobacco for such purposes.

Our goal is to design a social media intervention that could be delivered on a large-scale population basis. The CDC "30 Smoke-free Days" Facebook event and the Tips™ campaign both prompted a call to positive action, specifically to use free state quitline services, a scalable approach we will use in this study. Quitlines represent a high impact approach to improve access and availability of tobacco dependence treatments because of their potential to achieve wide reach into the population, including hard-to-reach subgroups. The AK quitline services consist of free coaching calls, web coaching, supportive text messaging program, personalized web-based quit plan, a quit guide and other written materials, and/or a two week starter supply of free nicotine patches, gum, or lozenges. Quitline coaches receive cultural competency training for coaching AN people.

However, we recognize it is important to also promote other types of treatment resources in the event that federal funding for state quitlines diminishes. Thus, we will additionally promote use of evidence-based quit smoking website resources ([smokefree.gov](http://smokefree.gov)) along with regional tribal tobacco treatment programs which provide phone counseling and access to stop smoking medications. Tribal programs vary on the number of counseling sessions and duration of free nicotine replacement therapy provided.

#### Health Communication Framework

We will use [name] cultural variance and surface/deep structure frameworks to address the influence of culture in designing health messages. Cultural variance framework considers AN cultural influences on health behaviors including specific beliefs, norms (i.e., communication styles, social acceptance of tobacco use), values (e.g., interdependence), and AN knowledge systems/ways of knowing. Surface and deep structure inform both content and format of messages. Surface structure involves matching materials and messages to observable social and behavioral characteristics such as AN people, music, and clothing. The second dimension (deep) incorporates cultural beliefs and values. Appropriate surface structure generally enhances receptivity, comprehension, and acceptance of messages whereas relevant deep structure conveys salience. Cultural variance framework largely addresses deeper level components of tailoring messages. We will use a planning framework based on

the NCI and CDC recommendations for developing social media and other digital health communication tools, addressing key components of message construction. This framework is in line with researcher recommendations to iteratively develop digital health interventions with user feedback. Thus, as part of our formative work we will conduct two rounds of qualitative (phase 1) then quantitative (phase 2) pre-testing to develop message concepts and develop the intervention. Next, the intervention prototype will be developed and beta-tested (phase 3).

## **Phase 1**

### **Qualitative Pre-Testing using Individual Interviews**

**Sample.** We will use a stratified purposeful sample of AN adult smokers with divisions based on audience segment (sex, age group [19-29, 30-49, 50+ years] and region [urban, rural]). Krueger recommends conducting at least 10-15 interviews per major subset before reaching data saturation, whereby no new information is being learned. We estimate about 40 individual interviews (20 men, 20 women; 20 urban, 20 rural; 12-13 within each age group) to achieve data saturation. Eligibility criteria for participants are described in Table 1 below. Various stakeholders will also be interviewed including AK quitline coaches, tribal cessation program counselors, and Alaska Education Advocacy members, with about 10 interviews total. There are no eligibility criteria for stakeholders, other than that they must be health professionals; stakeholders will be selected and approached for participation by the Mayo study team. The ANTHC Tobacco Cessation Program will obtain names and contact information of Tobacco Treatment Specialists and statewide Quitline personnel interested in being contacted for the interviews and provide them to the Mayo study team. Priority for stakeholder interviews will be based on length of time providing tobacco cessation counseling. Stakeholders will verbally consent and complete an interview similar to participants but it will be geared to health care professional views instead of those of an AN person who smokes.

**Procedures.** Interviews will be done by phone and last about 45 minutes, but may take as long as one hour. Participants will receive a \$25 Visa gift card as remuneration. Eligible participants who have provided verbal consent as described above will be emailed a password-protected link to view the materials online. Materials will be available for review online on the study web site and links to the materials will also be emailed to the participant. At the end of the interview the participant will be asked if he/she would like referral information for programs and services to quit smoking. If the participant is interested, the study coordinator will mail the participant information on the Alaska Quitline and local tribal tobacco cessation program.

**Moderator guide and training.** A semi-structured moderator guide was developed and a project coordinator at ANTHC will conduct the interviews. [name] and [name] will provide training for the project coordinator in Anchorage including 4 hours of didactic instruction, followed by 4 hours of mock interview practice, and a certified completion interview. All sessions will be audiotaped.

The interview will first cover a brief assessment of socio-demographics such as health literacy, age, sex, education, marital status, and tobacco use. The interview also covers:

(a) *Tips™ digital stories*: Review 4 stories from Tips™ (each about 30 seconds long) and obtain feedback. Participants will view online selected general audience videos (i.e., Terrie Bill, and Jessica's stories) and one video featuring an AN person with COPD (Michael's story) due to the strong emotional appeals about impacts of quitting on family members.

Link to CDC Tips™ videos: <https://www.cdc.gov/tobacco/campaign/tips/index.html>

- For each story: feedback is obtained on the storyteller and story characteristics, including identification and engagement; and cultural congruence (i.e., factual-based appeals from former smokers).
- Compare reactions for general audience stories versus the story featuring an AN person.

- Assess preferences for message source for new stories: AN person, sex, age, region, tobacco use, and relationship (e.g., grandparent, sibling, spouse or Elder).

(b) *ANTHC digital stories*: Participants will view two stories from the 7 videos below that feature AN people and are already developed by ANTHC. The research team will select 2 videos of potential videos listed below.

The video descriptions and online links are as follows:

1. Tania (community health aide, role model),  
time 1:38 <https://player.vimeo.com/video/55410351>
2. Edith (cancer, quit for family),  
time 2:33 <https://vimeo.com/160043666>
3. Casandra (cancer, dad quit, she quit for husband and son),  
time 2:33 <https://player.vimeo.com/video/55320782>
4. Caroline (chew tobacco),  
time 2:25  
<https://player.vimeo.com/video/55320781>
5. Marie (quit smoking for son),  
time 2:21  
<https://player.vimeo.com/video/55320784>
6. Caroline (role as tobacco prevention professional),  
time: 1:48 <https://player.vimeo.com/video/55320946>
7. Aubrey (she didn't start smoking until college and only smoked for a year, then quit),  
time: 1:38 <https://player.vimeo.com/video/62102834>

(c) *Other content for moderator postings (text and images)*: Four general audience postings from the CDC 30 Smoke-Free Days Facebook event will be viewed by participants that represent different themes, such as setting a quit date, celebrating milestones, family support, and cravings.

- The cultural relevance of postings is assessed and ideas for adapted or new content are gathered.
- Individual and cultural barriers to smoking treatment use or cessation that should be addressed; for example, beliefs about quitlines and stress/affective comorbidity are addressed.

(d) *Optimizing Facebook intervention engagement*: Finally the interviewer asks participants how to make the Facebook group more engaging (i.e., would text message prompts help?) and assess cultural need for groups separated by sex/age.

The stakeholder interview is similar except for brief demographic questions only and the feedback elicited is geared to health care professional views instead of those of an AN person who smokes.

Qualitative analyses. Sample characteristics will be summarized using descriptive statistics. Recordings will be transcribed by a professional transcription service. Content analysis supplemented by QSR NVivo software, version 10 (Doncaster, Victoria, Australia) will be used to generate response themes. All transcribed statements will be analyzed. Codes and categories will be developed based on moderator guide topics and themes emerging from the data. Two study team members will code responses independently for each topic area; inter-rater agreement (kappa coefficient) will be assessed. During this open-coding process, themes will be extracted for analysis when there is code endorsement or elaboration by several interviews. In addition to open coding, planned comparisons within and across sex, age, and region strata will be carried out and connections made between identified categories. Coding discrepancies will be resolved through discussion with a third study team member until consensus is reached.

Concept development. From the qualitative results, the research team will develop six test concepts: 3 storylines for the digital videos with written text and graphics, and 3 image/text moderator postings representing different types of appeals and message sources. We will consult with the ANTHC media department and Mayo social media department in developing these concepts.

**Inclusion/Exclusion Criteria:**

**Table 1:**

**Participant Eligibility Criteria and Rationale for Both the Formative Work and Pilot Trial: Phases 1-4**

Study Inclusion/Exclusion Criteria	Rationale
Alaska Native person (based on self-reported race/ethnicity) and resides in Alaska	Study targets a population with among the highest prevalence of tobacco use in the U.S. We chose to conduct this initial study in AK to reduce sample and intervention design heterogeneity. Across the nation, there is immense cultural and geographic variability, e.g., urban vs. reservation dwelling, ceremonial vs. non-ceremonial tobacco use. Also, AK has highest percentage of AN residents vs. all other states (19% vs. 2%).  If effective, the intervention could be adapted for and disseminated to AI/AN adults nationwide.
Age 19 years or older	Legal smoking age in AK is 19 years. Different social media venues and content may be warranted to address developmental issues among those $\leq 18$ years. A Twitter-based intervention for adult smokers 20-59 years found age was not related to engagement or cessation,  thus, we chose not to restrict the upper age limit.
Both men and women will be included	There are no preliminary data to indicate sex-specific interventions are warranted at this stage of the research. We will explore sex differences on feasibility and efficacy as a research question.
Smoked at least 1 cigarette per day over the past 7 day period	Allows for participation of AN people who smoke who report fewer cigarettes per day and are considered “light” smokers, but have cotinine concentrations equivalent to “heavy” white smokers, indicating differences in nicotine metabolism. 
If other tobacco use, cigarettes are the main tobacco product used	Cigarette smoking in combination with other tobacco product use is highly prevalent in some AK rural regions;  thus, results are more generalizable if other tobacco use is allowed.
Considering or willing to make a quit attempt	Intervention promotes treatment utilization and quitting. We will explore readiness to quit as a potential moderator of Facebook engagement and efficacy.
Has access to Broadband (high speed) Internet on mobile phone, at home, work, or other location.	Facebook can be accessed on a variety of technology devices such as computers, iPads, and mobile phones. Broadband internet access is needed to access social media and to upload and download videos and other links.
Has an existing Facebook account or willing to set up an account prior to study enrollment.	There is already good adoption of Facebook in rural regions of AK. Including participants familiar with regular social media interaction enhances participation, whereas non-users or those unfamiliar with Facebook are less likely to engage in the intervention.  To provide study access to a broader group, we will offer an online or paper-based tutorial for those without a Facebook account.
For past 3 months not enrolled in a program or using pharmacotherapy	Study promotes treatment uptake, utilization, and quitting.

## **Phase 2: Quantitative Pre-Testing of Prototype**

**Sample.** We will test the concepts developed in Phase 1 using quantitative survey interviews conducted with a new sample of 40 AN adult smokers (eligibility criteria described above) via a stratified purposeful sample with divisions based on audience segment (sex, age group, urban/rural region). Participants will receive a \$25 Visa gift card as remuneration.

**Procedures.** Respondents will view test concepts online through pictures and text embedded in the survey. If preferred, participants will be mailed or emailed the concepts for review in advance of the survey. The survey will be done online via Qualtrics survey software or by email or phone if preferred. The survey will take about 20- 30 minutes to complete. At the end of the survey the participant will be asked to indicate if he/she would like referral information for programs and services to quit smoking. If the participant responds Yes, the study coordinator will mail the participant information on the Alaska Quitline and local tribal tobacco cessation program.

**Measures.** The survey will include items assessing socio-demographics such as health literacy, age, sex, education, and marital status; tobacco use, and a validated measure of perceived effectiveness (PE) to pre-test each concept. PE is useful for assessing the likelihood of success of potential messages when large scale efficacy pretesting for behavioral impact is impractical. Measures of PE have been underutilized in the evaluation of message tailoring for subpopulations. We will use a 6-item validated measure of PE that was used to evaluate the Tips™ stories and similar to PE measures used in other smoking cessation research. After viewing each concept, respondents will rate their level of agreement on a scale from 1 (strongly disagree) to 5 (strongly agree) with the following statements: (1) this was worth remembering, (2) this grabbed my attention, (3) this was powerful, (4) this was informative, (5) this was meaningful, (6) this was convincing. Participants will also rate each concept for “this fits with my culture.” **Statistical analyses.** Sample characteristics and PE items will be summarized using descriptive statistics including means, percentages, and frequencies. The Chi-square goodness of fit test will be used to analyze concepts most and least preferred by participants. The association of participant sex, age, and region with message concept preferences will be examined using line regression.

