**Supplemental Aim: Quantitative**

We will use the information we have learned in our previous phases to adapt existing content on COVID-19 and smoking, and conduct quantitative testing of PE among a new sample of 40 AN smokers using identical procedures and evaluation process as was done in phase 2 of the study.

*Sample.* We will enroll 40 AN smokers recruited statewide, with stratifications based on audience segment (sex, age, and location – rural or urban). Recruitment procedures and study eligibility criteria are described above. Participants meeting the eligibility criteria will be provided with details on the study and asked to provide verbal consent. Participants will receive a \$25 gift card for their time.

*FB Content.* We will use existing content (i.e., text, videos, images) on COVID-19 and smoking for adaptation from the ANTHC media department, Tips™ Campaign, and the U.S. FDA Center for Tobacco Products social media content. Informed by the cultural variance and surface/deep structure health communication frameworks, the qualitative work completed previously provided insights into cultural tailoring for new content on COVID-19 and smoking. Qualitative analyses indicated that participants preferred culturally relevant content that included images of AN people, places, and activities that told a compelling story and was emotional. Participants tended to have less interest in content that was not relatable or that included individuals who were not AN. If a story was not AN, then it needed to include AN values, such as including family/children or telling a story in a ‘real’ way, with emotion and honesty. **Figure 1** below provides an example of how we modified existing content in the parent R34 grant to be relevant to the AN culture.

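### Phase 2 rests its only inferential analyses on an undefined preference outcome, and plans no within-person comparison of the ratings it collects on all six concepts

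*Combined protocol and SAP*

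**What the plan says.** Under Concept development in the Phase 1 section, "the research team will develop six test concepts: 3 storylines for the digital videos with written text and graphics, and 3 image/text moderator postings". Phase 2 tests these through "quantitative survey interviews conducted with a new sample of 40 AN adult smokers".

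The Phase 2 Measures text describes a survey covering socio-demographics, "tobacco use, and a validated measure of perceived effectiveness (PE) to pre-test each concept". Each person rates every concept: "After viewing each concept, respondents will rate their level of agreement on a scale from 1 (strongly disagree) to 5 (strongly agree"), on six PE statements. A seventh item, cultural fit, is collected at the same level ("Participants will also rate each concept for" it). No most-preferred, least-preferred, ranking or forced-choice item is listed, and no rule turns ratings into a preference.

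The Phase 2 statistical paragraph summarises the PE items descriptively and gives the cultural-fit item no analysis. It then has two inferential statements. The first is about which concepts stand out: "The Chi-square goodness of fit test will be used to analyze concepts most and least preferred by participants". The second turns to audience segments, and it is the one that names a regression: "The association of participant sex, age, and region with message concept preferences will be examined using line regression".

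The last term is read here as linear regression. No within-person method is named, and no error rate, effect size or SD is given for Phase 2.

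The Supplemental Aim is said to test PE "using identical procedures and evaluation process as was done in phase 2 of the study". Its own Procedures and Statistical Methods nevertheless define a total PE score (the mean of the six items) and relate that score and the cultural item to sex, age group and locality by Kruskal-Wallis test. It has no preference test.

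**The concern.** The outcome of both planned tests is missing from the plan. Without a definition, an analyst cannot tell whether preference is one pick per person, a score per concept, or a pooled set of scores, and the suitability of linear regression depends on which it is. The neighbouring goodness-of-fit statement makes a categorical pick the natural reading, and that is the reading under which linear regression fails.

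Meanwhile the validated PE scores, measured six times on each person, receive no inferential comparison between concepts. Phase 2 is the quantitative pre-testing step that feeds the intervention content. What is at stake is how reliably it shows which concepts work better and whether any segment responds differently.

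**Working it through.** **Inputs from the documents.** n = 40 people; k = 6 concepts; six PE items per concept on a 1-5 scale, plus one cultural-fit item. Phase 2 has no power figure to reproduce.

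**Assumed inputs (none are in the documents).** Two-sided alpha 0.05; one concept better than the other five by 0.3 to 0.5 points; between-person SD 0.4 to 0.6; person-by-concept SD 0.5 to 0.8; item noise SD 0.6.

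**1. Data collected.** PE ratings per person: 6 × 6 = 36, so 40 × 36 = 1,440. With the cultural item: 6 × 7 = 42, so 40 × 42 = 1,680. A top-pick analysis uses 40 picks.

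**2. Goodness of fit with one pick per person.** Expected count per concept is n/k = 40/6 = 6.7. Simulated type I error was 4.4% to 5.7%. The test is valid.

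**3. Linear regression on a nominal pick.** Take an illustrative table of top picks for concepts A to F: 8, 2, 3, 3, 2, 2 in 20 men and 2, 8, 2, 2, 3, 3 in 20 women. Only the numbering of the concepts is changed.

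- A=1, B=6, C=2, D=3, E=4, F=5: means 53/20 = 2.65 and 87/20 = 4.35. Each group's sum of squares is 60.55, so the pooled variance is 121.1/38 = 3.187 and SE = √(3.187 × (1/20 + 1/20)) = 0.565. Then t = 1.70/0.565 = 3.01 and p = 0.005.
- A=2, B=3, C=5, D=6, E=1, F=4: means 65/20 = 3.25 and 65/20 = 3.25, so p = 1.0.

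Over all 720 numberings p runs from 0.005 to 1.0, and 20% fall below 0.05. The chi-square test of the same table, which does not depend on numbering, gives p = 0.16.

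**4. Linear regression on pooled scores.** If the regression uses 40 × 6 = 240 person-by-concept rows and ignores clustering, the design effect for sex is 1 + (6 − 1)ρ. Approximate type I error is 2[1 − Φ(1.96/√design effect)].

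| Assumed within-person correlation ρ | Design effect | Formula | Simulated (4,000 runs) | Simulated, person means |
|---|---|---|---|---|
| 0.20 | 2.00 | 16.6% | 16.0% | 4.5% |
| 0.35 | 2.75 | 23.7% | 23.9% | 5.6% |
| 0.50 | 3.50 | 29.5% | 30.5% | 5.2% |

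Regression on person means, or on one concept's score at a time, avoids the problem. The plan specifies neither.

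**5. Sensitivity of the pick against the ratings.** Simulated power (1,500 runs per setting), with the pick taken as each person's top-scoring concept and ties broken at random:

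| Between-person SD / person-by-concept SD | Difference | Goodness of fit | Friedman | Repeated-measures ANOVA |
|---|---|---|---|---|
| 0.6 / 0.6 | 0.3 | 22% | 38% | 45% |
| 0.6 / 0.6 | 0.4 | 44% | 66% | 72% |
| 0.6 / 0.6 | 0.5 | 61% | 87% | 91% |
| 0.6 / 0.8 | 0.4 | 27% | 44% | 49% |
| 0.6 / 0.8 | 0.5 | 39% | 62% | 70% |
| 0.4 / 0.5 | 0.3 | 35% | 54% | 61% |
| 0.4 / 0.5 | 0.4 | 59% | 80% | 87% |

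**6. Information kept.** Each power was converted to the noncentrality of a 5-df chi-square test at 0.05, and ratios were taken. Over these seven settings goodness of fit keeps 0.56 to 0.65 of the Friedman information and 0.47 to 0.55 of the ANOVA information.

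**The case against.** The other side has real points.

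- A reader might infer that both preference tests are invalid. They are not: goodness of fit is a standard test for a nominal choice and holds its error rate here.
- A reader might infer that most of the information in the ratings is thrown away. This is not shown. PE is still described, and the pick keeps roughly half to two-thirds of the information under the assumed inputs.
- A reader might infer that preference has to be derived from the ratings. The Measures text says what the survey will include, without claiming to be exhaustive, so a direct most/least question may exist. The power comparison in step 5 would then not describe it.
- The plan never says that preference is nominal. If it means one concept's score, linear regression on sex, age and region is usable.
- Phases 1-3 are declared exploratory with no hypothesis, Phase 2 states no selection rule, and the prototype is beta-tested afterwards.
- With 40 people, a full set of concept-by-factor terms means 5 × (1 + 2 + 1) = 20 interaction parameters, which can only be exploratory.

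All of this limits the size of the point. It does not supply the missing outcome definition, show that the regression is appropriate on its natural reading, or provide a within-person comparison of the ratings.

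**Conclusion.** The point stands as a cheap improvement to a formative analysis. Preference is undefined and has no listed item. Linear regression is unsuitable if it is a nominal pick, and its type I error is about 16% to 31% if ratings are pooled without clustering at correlations of 0.2 to 0.5. Goodness of fit is valid but, when the pick comes from the ratings, clearly less sensitive than a within-person test. The error rates and power figures rest on assumed SDs, correlations and effect sizes; their direction was the same in every setting shown.

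Two further inferences are not supported. The wording about identical procedures might suggest that the Supplemental Aim inherits these tests. It does not, because its Statistical Methods set out a different analysis of a defined PE score. Nor does anything here touch the pilot trial's endpoints.

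**What to change.** - Make the total PE score per concept, as defined in the Supplemental Aim, and the cultural-fit item the Phase 2 outcomes.
- Compare concepts within person with a linear mixed model (concept fixed, random participant intercept) or a Friedman test. Report concept means with 95% confidence intervals.
- In place of linear regression on preference, examine sex, age group and region as exploratory terms, one factor at a time (5, 10 and 5 interaction terms) or separately per concept.
- If a direct most/least-preferred item exists, list it, keep goodness of fit with one pick per person, and use an exact categorical test for its association with sex, age group and region. A full multinomial model, with 5 × 4 = 20 slopes, is too large for 40 people.
- If Phase 2 is complete, re-run it on the existing ratings. The Supplemental Aim analysis need not change on account of this point.

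The cost is a revised paragraph and a little analysis work, with no new data. Subgroup estimates from 40 people will be imprecise and should be reported as such.
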